3. Laboratory for Biological Probes Radiolabeled with High and Low-Energy Isotopes: Negative flow safety hood and volatile radioisotope absorption system with activated carbon, orbital shaker, visible light microscope, and safety cabinet for storing and decaying radioactive waste.
4. Flow Cytometry Room: Flow cytometer (FACSort), analysis computers.
5. Darkroom for Radioautographic Processing will be available, including a Polaroid camera, developing reagents, and radioautography cassettes.
6. Washing, Sterilization, Distilled Water, and Ice Room: Material drying oven, floor autoclave, flake ice maker, water distillers, water deionizer, ultra-pure water production system.
7. A Central Laboratory containing pH meters, a spectrophotometer, an ELISA reader, and a 10-head gamma counter will be available.
8. Immunology Library includes ten journal subscriptions, a database for bibliographic reference search, and over 100 immunology and related books.
9. Others: Word and graphics processing computer systems, fax, direct phone line, email, and internet access.
10. Central Services: In addition to the infrastructure within the Immunology Program, the Faculty of Medicine has other general-use equipment that may be relevant to this project, such as an ultra-centrifuge, scintillation counter, confocal microscope, peptide, and oligonucleotide synthesis and sequencing, among others. There is also a central animal facility designed for maintaining pure strains of mice, infected and immunized mice, and rabbits.
11. Clinical Hospital of the University of Chile: The infrastructure of the blood bank at the Clinical Hospital of the University of Chile is available, featuring equipment for leukapheresis sample collection and the Cryopreservation Laboratory equipped with a modern automated biological sample freezing system.
12. Associated Companies in the Project: Oncobiomed Ltda., Oncomed Ltda., and Tecnofarma S.A. have provided their clinics for the selection and treatment of some patients and their administrative teams for technological transfer, respectively.

Funding:

This study will be financially supported through contributions from the FONDEF Project No. DO2I1088: "Research and Development of Biological Vaccines for Oncological Immunotherapy," for 310 million Chilean pesos, for a duration of three years (2003-2005). Additionally, the project's associated companies,

ONCOMBIOMED Ltda. (85 million Chilean pesos) Furthermore, Tecnofarma S.A. (35 million Chilean pesos) has committed to providing funds through personnel financing and cytokine grants such as IL-2.

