 - In vitro response: ELISPOT assays, measuring IFN- γ production in the peripheral blood of treated patients. Compare specific immune responses after each therapy cycle by measuring IFN- γ production by tumor-specific CTLs. Radioactive chromium releases cytotoxic assays to measure CTL and NK-mediated antitumor response. After each therapy cycle, ELISA assays for quantifying cytokines (IFN- γ , IL-10) in patient serum.
- **CLINICAL RESPONSE MEASUREMENT:** To observe the objective response rate. The percentage of patients with complete response (CR) and patients with partial response (PR) will be reported.

SECONDARY SPECIFIC AIMS:

To evaluate:

- Overall Survival.
- Disease-Free Survival.
- Quality of Life (assessed using EORTC global QLQ-C30 and EORTC disease-specific QLQ).
- Performance status response: The percentage of patients with a 20% or more significant increase in activity measured by the Karnofsky index will be reported.

MATERIAL AND METHODS

Dendritic Cell Generation: Patient leukocytes will be obtained through leukapheresis at the Blood Bank of the Clinical Hospital of the UNIVERSITY OF CHILE, following the standard protocols used in that unit. Peripheral blood mononuclear cells (PBMCs) will be isolated from peripheral blood using a Ficoll-Hypaque gradient. PBMCs will be cultured for 2 hours at 37°C and 5% CO₂ in a suitable serum-free clinical research medium, AIM-V Clinical Research® (Life Technologies, USA). Non-adherent cells will be discarded, and adherent cells (monocytes) will be cultured in AIM-V supplemented with 500 U/ml of recombinant IL-4 (R&D Systems, INC., MN, USA) and 800 U/ml of GM-CSF (R&D Systems, INC., MN, USA). On the sixth day, monocytes differentiated into dendritic cells will be pulsed with melanoma extracts and then matured with TNF- α (R&D Systems, INC., MN, USA). Flow cytometry will confirm mature dendritic cells' CD14⁻, CD36^{low}, and CD83^{high} phenotype characteristics. Mature DCs will be washed twice and resuspended in 300 μ l of sterile saline. All cell manipulation procedures for vaccine production will be performed under GMP conditions, as indicated.

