ELISA ASSAY FOR THE DETERMINATION OF IL-10 AND IFN γ IN PATIENT SERUM: In brief, plates sensitized with primary anti-IFN- γ monoclonal antibody (acMo) (OptEIA, Pharmigen) and primary anti-IL-10 monoclonal antibody (acMo) will be blocked with 1% PBS/BSA for 1 hour at room temperature. Then, 100 μl of each patient's serum will be added to each well and incubated for 2 hours at room temperature. The wells will then be washed and incubated for one hour at room temperature with 100 μl of secondary antibody (0.75 $\mu\text{g}/\text{ml}$ biotin-conjugated anti-IFN- γ acMo Avidin-HRP (Pharmigen)). Substrate (TMB and hydrogen peroxide) will be added for 30 minutes at room temperature in the dark. The wells will then be washed, and the STOP solution will be added. Absorbance at 450 nm will be read using an ELISA reader (BIORAD, model 3550) at the Disciplinary Program of Immunology at the ICBM, University of Chile.

Dose and Dosing Rationale: Selected patients will be treated with four cycles of therapy over 60 days. In each dose, 10 to 20 $\times 10^6$ DCs loaded with extracts from 3×10^6 allogeneic melanoma cells will be injected. The extracts will be prepared from irradiated melanoma cells lysed through continuous freezing, thawing, and sonication. This dose is estimated to be sufficient to induce an antitumor immune response, as preclinical and clinical trials have demonstrated clinical and Laboratory immune responses, supporting the method's safety. To support the patient's immune system stimulation, interleukin-2 (IL-2) will be administered subcutaneously at 2.4×10^6 IU/m² two days after the second vaccine dose for three consecutive days. This regimen will be repeated after each vaccination. Currently, standard protocols administer between 18×10^6 and 9×10^6 IU/m² of IL-2 per dose (recommended by distributor CHIRON BV Holland). The low doses used in this study are based on the project director's experience, supported by studies published in international journals and recent literature (67-70). The intention is to avoid IL-2-mediated side effects while preserving its beneficial effects.

Treatment:

- a) Treatment Regimen: For administering each dendritic cell dose, the treating investigator will observe and treat patients on an outpatient basis in an adequately equipped outpatient clinic. The 300 μl dose in a sterile saline solution will be injected subcutaneously, preferably near the primary tumor or near unaffected lymph nodes.

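### The serum ELISA as written names no detection antibody for IL-10 and washes the wells after colour development, so it cannot give the cytokine values the aims require

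*Protocol*

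**What the plan says.** The in vitro response item of the protocol's specific aims, listed ahead of the secondary aims, asks for "ELISA assays for quantifying cytokines (IFN- γ , IL-10) in patient serum" after each therapy cycle. Under Patient Monitoring, blood for the ELISPOT and ELISA assays is drawn before each vaccination.

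The method is in Material and Methods, in the paragraph that opens "ELISA ASSAY FOR THE DETERMINATION OF IL-10 AND IFN γ IN PATIENT SERUM: In brief". It coats plates with a primary anti-IFN-γ antibody and a "primary anti-IL-10 monoclonal antibody (acMo) will be blocked with 1% PBS/BSA for 1 hour at room temperature". Serum is then added, and after a wash a single secondary reagent is given, "biotin-conjugated anti-IFN- γ acMo Avidin-HRP (Pharmigen", for one hour. The rest runs in this order:

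- TMB with hydrogen peroxide is left on for half an hour, protected from light.
- Next comes this instruction: "The wells will then be washed, and the STOP solution will be added".
- Only after that does the plate reader take its measurement, at 450 nm.

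No other part of the protocol shown names an anti-IL-10 detection antibody or gives a different order of steps.

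**The concern.** The paragraph is meant to measure two cytokines, but its reagents can detect only one, and the order of its last steps removes the signal for that one too. These are positive instructions, not omitted detail: the text gives a concentration, volumes, times, a wavelength and a reader model.

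At stake is the serum cytokine part of the immune response assessment. The background section lists IL-10 among the immunosuppressive substances by which tumours escape recognition, so the IL-10 series bears on an obstacle that the protocol itself raises. A laboratory that followed the text would have no usable values for that series, nor for serum IFN-γ.

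**Working it through.** There is no statistical figure to reproduce. The check follows the written steps and compares them with the assay's purpose and with the neighbouring ELISPOT paragraph.

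**Detection antibody**

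| Step | IFN-γ | IL-10 |
|---|---|---|
| Required by the aims | yes | yes |
| Capture antibody named | yes | yes |
| Detection antibody named | yes, biotin-conjugated | none |

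A sandwich ELISA reports a cytokine only if the detection antibody binds that cytokine. IL-10 held by its capture antibody would meet only an antibody to IFN-γ. With separate plates, the IL-10 wells would show background. If both capture antibodies share a well, any signal would reflect IFN-γ. In neither case is IL-10 quantified.

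**Order of steps**

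| Order | ELISA text | ELISPOT text |
|---|---|---|
| 1 | Secondary antibody and Avidin-HRP | Secondary antibody, then streptavidin-ALP |
| 2 | (no wash described) | Wash |
| 3 | TMB substrate, 30 minutes | NBT/BCIP colour reagent, 5 minutes |
| 4 | Wash | (none described before counting) |
| 5 | STOP, then absorbance at 450 nm | Spots counted by microscope |

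The ELISPOT washes before the colour reagent and counts spots that stay in place. The ELISA washes after the colour reagent and then reads absorbance. I assume that the TMB product is in solution. This is general assay knowledge that the protocol does not state, but it fits a plate-reader measurement after STOP. On that assumption the late wash empties the signal from every well, for both cytokines.

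The missing earlier wash also matters. Without it, unbound enzyme is still in the well when the substrate goes in, so colour would form whether or not cytokine was captured. Deleting the late wash alone would therefore not repair the method.

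**Number of samples**

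- Stated: four cycles, with one sample before each vaccination, gives 4 per patient who receives all four.
- At 30 patients: 4 × 30 = 120 per cytokine.
- If enrolment stops at 20 patients: 4 × 20 = 80.
- If enrolment stops at 12 patients: 4 × 12 = 48.
- A fifth sample, after the last cycle, is suggested by "After each therapy cycle, ELISA assays for quantifying cytokines". However, the end-of-treatment list mentions in vitro immune assays without naming the ELISA. If that sample is taken, the count at 30 patients is 5 × 30 = 150 per cytokine. I treat this as an upper figure for 30 patients.

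**The case against.** The strongest reply is that this is a slip in a summary, not a plan to run a broken assay. The paragraph is marked as brief and cites a commercial reagent line. The secondary antibody's concentration and label match those in the ELISPOT paragraph, so the words may have been copied across. The wash looks transposed, since it is absent where one would expect it and present one step later. Text may also have dropped out around the secondary reagent, where the antibody and the Avidin-HRP run together with no connecting word. All of this is plausible and I accept it. It explains the error but does not correct it, because nothing else in the protocol gives the right antibody or order.

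Two stronger readings are tempting, and the documents support neither.

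- *A reader might infer that the trial's serum cytokine data are invalid.* The protocol shows what was written, not what was done at the bench, and practice may have differed.
- *A reader might infer that IL-10 would be silently false negative in every patient and then be reported as absence of immunosuppression.* Quantifying a cytokine implies known standards, although the paragraph does not describe them. With the wrong detection antibody the IL-10 standards would be flat as well, and with the colour washed away every well would be blank. That would probably be noticed as a failed run. Nor does the protocol state any plan to infer immunosuppression from serum IL-10, which it mentions only as background.

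The objection that the reach is limited also stands. The Statistical Analysis section gives the primary objective as objective response and toxicity, and serum cytokines are one of several immune readouts.

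**Conclusion.** The point holds as an error in the written procedure. As printed, the method cannot quantify IL-10, because no antibody that detects it is named. It would also lose the IFN-γ signal, because the wash falls between colour development and reading. The first conclusion needs only the principle of a sandwich assay; the second rests on the TMB product being soluble.

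The extent is the serum cytokine readout alone: at least four samples per fully treated patient, or 120 per cytokine at 30 patients, and fewer if the study stops early. Objective response, the rules for stopping at 12 and 20 patients, and the sample size do not depend on it. The likely cause is drafting, and how the assay was actually run remains an open question.

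**What to change.** Change the ELISA paragraph in two places and add one check.

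1. Name a matched biotin-conjugated anti-IL-10 detection antibody for the IL-10 wells, and keep the anti-IFN-γ antibody for the IFN-γ wells.
2. Move the wash so that it follows the Avidin-HRP step and precedes the substrate. STOP then goes directly into the developed substrate and the plate is read at 450 nm. The wash should be moved, not simply deleted.
3. Before any serum IL-10 or IFN-γ value is reported, confirm from laboratory records which antibody and which order of steps were used. Values from runs done as printed should not be reported. The protocol describes cryopreserved cells but no stored serum, so repeat testing cannot be assumed possible.

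The cost is two corrected lines, one matched reagent and a look at the laboratory records. It adds no blood draws or visits.

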- b) Immediately after treatment, the patient must be monitored. Vital signs should be taken 15 minutes before and after each treatment, and the patient should be observed in the clinic for at least one hour. After the observation period, the patient will be sent home.
- c) Interleukin-2 will be administered subcutaneously, on an outpatient basis, in a properly equipped outpatient clinic for three consecutive days. Vital signs will be monitored, and the patient will be observed in the clinic for 30 minutes.
- d) Patients will be followed to detect and evaluate potential toxic reactions to treatment. The next dose can be repeated the following week if: - There was no grade IV toxicity with the previous treatment, - There was no obvious disease progression - The patient does not meet the exclusion criteria for the protocol.

Inclusion Criteria:

- Patients with histologically confirmed melanoma of the skin: Breslow, Clark, histological type. Location of the primary, clinical, or pathological regional status.
- Complete staging demonstrating the presence of distant metastases, either visceral or in soft tissues or bone tissue: Brain, Lung, Abdomen, and Pelvis CT and bone scintigraphy.
- Objectively measurable disease by clinical or radiological means
- Karnofsky's Performance Status is more significant than 70%
- Life expectancy greater than three months
- Patients over 18 years old
- Informed consent from the patient to participate in the protocol

Exclusion Criteria:

Patients meeting any of the following criteria will be removed from the study:

- Age greater than or equal to 65 years
- Ongoing active infections, including viral immunodeficiency
- Previous chemotherapy within less than two months
- Concomitant malignant tumors (e.g., Chronic Lymphocytic Leukemia, etc.)
- Uncontrolled concomitant diseases (Hypertension, unstable Diabetes mellitus, renal diseases requiring dialysis)
- Situations or conditions requiring urgent surgical intervention, such as intestinal obstruction due to metastasis
- Pregnancy or lactation
- Concurrent participation in other therapeutic research protocols
- Any condition that compromises the objectives of this study.

Removal Criteria from the Study:

Patients will be removed from this study if any of the following conditions occur:

- By the patient's decision to discontinue the study.
- Intolerable adverse reactions, according to WHO Criteria Grading Toxicities

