- Intercurrent illness that may compromise the patient's life or interfere with the treatment study evaluation
- Requirements for concomitant medication that may interfere with study results.
- Failure to complete the study entirely
- Failure to follow up on the patient.

Sample Size

Recruitment will be conducted to terminate the study after a specific number of patients have been enrolled if a minimum number of responses have not been observed. The lowest significant response rate will be 20% ($\alpha = 0.10$; $\beta = 0.10$). If at least the minimum number of objective responses are observed to complete recruitment, 30 evaluable patients will be enrolled. For example, if there is no response in any of the first 12 treated patients or only 1 out of the first twenty, the study should be terminated. The confidence interval for the response rate is $>20\%$.

Evaluable Patient: An evaluable patient meets the inclusion criteria, does not meet any of the removal criteria, receives all four vaccination cycles, and has been clinically and radiologically followed until the end of this trial.

Study Conduct

- Signing of informed consent
- Complete medical history
- Complete physical examination
- Karnofsky Performance Status measurement
- Estimation of survival quality using the EORTC scale
- If applicable, photographs of the tumor and metastases
- Hematological studies, including albumin and total proteins.
- Electrocardiogram
- CD3, CD4, CD8 cell counts, and total lymphocyte count
- Blood sample collection for in vitro immunological studies.
- Staging radiological studies: Computed tomography of the brain, lungs, abdomen, and pelvis, and bone scintigraphy
- Estimation of metastasis size through physical and radiological examination
- Delayed hypersensitivity test (DTH)

Enrollment

After the procedures mentioned above, each eligible patient will be enrolled. Each patient will be given an identification number. Data will be maintained in a computerized file with restricted access for the research team for each patient.

Patient Monitoring

Patients will be clinically monitored once a week through the following parameters:

- Weight
 - Karnofsky Index
 - Vital signs
 - EORTC Quality of Life Index
 - Comprehensive physical examination
 - Monitoring for toxicity symptoms according to WHO Criteria Grading Toxicities and reporting adverse effects

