- Additionally, they will be evaluated through ELISPOT and ELISA assays, with blood samples taken before each vaccination, to assess the response of specific CTLs to DC stimulation and the presence of cytokines in the patient's serum.

Measurement at the End of Treatment

- Clinical evaluation of the patient
- Estimation of clinical or radiological tumor response: determining tumor volume
- Comprehensive physical examination
- Karnofsky Index
- Photography
- Quality of life and pain assessments
- Delayed hypersensitivity test (DTH): for in vivo response measurement
- Hematological and chemical tests: Assays for measuring in vitro immune response.

Long-Term Follow-Up

Once the patient has completed the full four-cycle treatment, they must be followed up every four weeks for one year. Every two months during the second year. The date of death must be determined in applicable cases. During each visit:

- Directed physical examination
 - Karnofsky Index
 - Estimation of clinical and radiological tumor size
 - Photography
 - EORTC Quality of Life Assessment
 - Reporting of adverse effects
- Clinical Response Assessment

TUMOR RESPONSE CRITERIA

CR: Complete disappearance of the tumor

PR: Tumor regression > 50%

MR: Tumor regression > 25% - <50%

SD: Decrease or growth < 25%

PD: Increase in tumor size during treatment

Statistical Analysis

The primary objective of this study is to estimate the objective response and toxicity associated with treatment using dendritic cells loaded when administered to patients with disseminated melanoma. A stratified recruitment design will be used in this study. In the first stage, 12 patients will be enrolled and treated with loaded dendritic cells. If none of the patients responds to the treatment, enrollment for this study will be terminated. If at least one patient responds to the treatment, the treatment will continue. If, after the enrollment of patient number 20, at least two patients respond to the treatment, the study should continue until a minimum of 30 evaluable patients with 3 out of 4 completed cycles. Assuming that the study will be completed with thirty patients as planned, the 90% confidence interval for the estimated response rate will be 12%, assuming a 20% response rate. If sufficient evidence indicates that the valid response rate is greater than 20%, it would be given if the lower limit of the confidence interval is more significant than 0.20 (alpha = 0.05, 1-tailed -test).

Primary Efficacy Analysis

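### Re-dosing depends on the absence of grade IV toxicity, but the visible schedule names no blood count, creatinine or bilirubin at the two checks that follow IL-2 (minor, cheap to fix)

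*Protocol*

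**What the plan says.** **Re-dosing rule.** Treatment item d of the protocol lets the next dose follow a week later if three conditions hold. The first is "There was no grade IV toxicity with the previous treatment". The others are no obvious progression and no exclusion criterion met.

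**Dosing.** Dose and Dosing Rationale sets four cycles over 60 days. IL-2 is given subcutaneously at 2.4 × 10⁶ IU/m² for three consecutive days, starting two days after the second vaccine, and again after each later vaccine.

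**Monitoring during treatment.**
- Vaccine visits (Treatment item b): "Vital signs should be taken 15 minutes before and after each treatment", plus at least an hour in the clinic.
- IL-2 visits (item c): "Vital signs will be monitored, and the patient will be observed in the clinic for 30 minutes".
- Weekly (Patient Monitoring): weight, Karnofsky index, vital signs, EORTC quality of life, physical examination, and "Monitoring for toxicity symptoms according to WHO Criteria Grading Toxicities and reporting adverse effects".
- Blood (Patient Monitoring): ELISPOT and ELISA, "with blood samples taken before each vaccination, to assess the response of specific CTLs to DC stimulation and the presence of cytokines".

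**Laboratory tests outside treatment.** The baseline list under Study Conduct has "Hematological studies, including albumin and total proteins". Measurement at the End of Treatment has "Hematological and chemical tests: Assays for measuring in vitro immune response".

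**Objective.** Statistical Analysis states: "The primary objective of this study is to estimate the objective response and toxicity associated with treatment".

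**The concern.** A rule that stops dosing at grade IV toxicity can act only on toxicity that someone has measured. Symptoms, vital signs and physical examination will reveal hypotension, fever or vomiting. They will not reliably reveal a low platelet count or a raised creatinine or bilirubin, which are graded from laboratory values and can be silent. The protocol's own Table 1 lists these among the effects of IL-2.

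Two things are at stake. The first is the safeguard: following the visible schedule as written, a silent laboratory toxicity after the first or second IL-2 course reaches the item d check only if an investigator happens to order a test. The second is the toxicity estimate, which is part of the primary objective: an abnormality that resolves before the end of treatment is not counted. Ad hoc testing would also make ascertainment uneven between patients.

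IL-2 is what this protocol adds to the completed phase I vaccine study, so its laboratory safety in the combination is something the trial should document rather than assume.

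**Working it through.** **1. Which checks follow IL-2.** Assume one vaccine per cycle.
- IL-2 courses follow vaccines 2, 3 and 4: 3 courses × 3 days = 9 injections.
- Re-dosing checks fall before vaccines 2, 3 and 4. The one before vaccine 2 follows dendritic cells alone, so 3 − 1 = 2 checks follow IL-2.
- Those two checks come after 2 × 3 = 6 of the 9 injections. The third course is followed by the end-of-treatment measurement, when no re-dosing decision remains.

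**2. What is scheduled at those checks.**

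| Time | Blood count | Creatinine, bilirubin |
|---|---|---|
| Baseline | Haematology listed | Not named |
| Vaccine and IL-2 visits | Not named | Not named |
| Weekly monitoring | Not named | Not named |
| Draw before each vaccine | Not named; immune assays only | Not named; immune assays only |
| End of treatment | Haematology listed | Chemistry listed, analytes not named |

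The end-of-treatment line joins its laboratory tests to in vitro immune assays, so safety chemistry there is probable rather than certain. The protocol names haematology where it intends it, and it does so only at the two ends of treatment.

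**3. Extent of the gap.** With the 30 planned evaluable patients:
- all four cycles given: 30 × 2 = 60 patient-checks after IL-2;
- only three vaccines given to each patient (Statistical Analysis mentions 3 of 4 completed cycles): at least 30 × 1 = 30. A patient stopped at the check before vaccine 4 has still had that second check, so 30 is a floor.

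**4. What Table 1 shows, and at what dose.** The grade 4 counts in 525 patients reproduce the printed percentages:
- bilirubinemia 13/525 = 2.48% (printed 2%);
- creatinine increase 5/525 = 0.95% (printed 1%);
- thrombocytopenia 5/525 = 0.95% (printed 1%);
- anemia 1/525 = 0.19% (printed 0%).

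The Interleukin-2 section ties Table 1 to intravenous treatment at 18 million units/m². The trial gives 2.4 million IU/m² subcutaneously, and 18/2.4 = 7.5. The documents give no rate for these toxicities at the trial dose, so no expected number of events is derived here.

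**5. What a test at the existing draw could detect.** Take the vaccine as day 0. IL-2 then falls on days 2, 3 and 4. If the next vaccine comes on day 7, the draw is 7 − 4 = 3 days, about 72 hours, after the last injection. If the four cycles are spread evenly over 60 days (60/4 = 15 days apart), it is 15 − 4 = 11 days after. The Interleukin-2 section says that in most patients the effects are under control within 72 hours of finishing treatment. A test at this draw would therefore detect mainly persistent abnormalities.

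**The case against.** **The tests may be named in text we cannot see.** The available protocol breaks off inside Table 1 and resumes partway through the specific aims. No toxicity aim is visible although toxicity is a primary objective, so one may stand in the missing part and may name laboratory tests. This limits the point. A reader might infer that the trial plans no safety laboratory work during treatment; the document does not support that. If the missing part names the tests, what remains is to carry them into the monitoring lists.

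**Other wording could cover it.** Item d promises follow-up for toxic reactions without limiting it to symptoms, WHO grading includes laboratory grades, and nothing forbids tests on clinical indication. Item d's exclusion-criteria condition and the removal criteria are further safeguards. All true, but none supplies a value: a grading scale schedules no blood test, and a silent abnormality prompts no order.

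**The risk is low at this dose.** This largely stands. The protocol states that low-dose subcutaneous IL-2 almost removes adverse effects. A reader might take the Table 1 rates into this trial: 13/525 to 24/525, depending on overlap between the four toxicities, would give 0.74 to 1.37 patients in 30. That is not supported, because the dose and route differ. Scaling the risk in proportion to dose would be an assumption without a source.

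**The remedy is partial.** Also true. A draw about three days or more after the last injection may miss transient changes.

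**This could be left to the analysis plan.** It could not. Safety sampling and the information needed for a re-dosing decision belong in the protocol.

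**Conclusion.** The point holds as a minor one. On the visible text, item d depends on toxicity grade, yet the schedule names none of the laboratory values needed to grade platelet, haemoglobin, renal or hepatic toxicity at the two checks that follow IL-2. Such toxicity could pass the rule unseen and be under-counted in part of the primary objective.

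The size is two checks per patient, between 30 and 60 patient-checks in 30 patients. This counts exposure to the gap; it does not show harm or quantify bias. No sample size, alpha or power figure is affected.

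The conclusion assumes one vaccine per cycle, IL-2 after vaccines 2, 3 and 4 only, and that the missing part of the aims does not already schedule these tests. It claims no excess of toxicity at 2.4 million IU/m².

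**What to change.** Add a blood count with platelets, creatinine and bilirubin at three places: the baseline list under Study Conduct, the blood draw already taken before each vaccination, and the end-of-treatment list. In the last of these, separate safety chemistry from the immune assays. Grade the results by the WHO criteria already named, and have item d require that they be reviewed before the next dose. If the missing text already names these tests, copy them into these lists and add the review requirement.

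The cost is two or three protocol lines and routine tests, on draws that already take place during treatment. The downsides are the price of the tests and an occasional dose delayed while results are awaited. Because of its timing, the pre-vaccination sample will detect mainly persistent abnormalities and may miss transient ones, so the report should not present it as complete capture of laboratory toxicity.
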